# 8.5 Accountability of Study Drug Supplies

All material supplied is for use only in this clinical study and should not be used for any other purpose.

The PI is responsible for study drug accountability, reconciliation, and record maintenance at the clinical facility. In accordance with all applicable regulatory requirements, the PI or designated trained site staff must maintain study drug accountability records throughout the course of the study. This person will document the amount of study drug received by the pharmacy and the amount dispensed to, administered to, and returned by participants, if applicable. The shipment/receipt records as well as records of dispensing, administration and return will be verified by a second member of the site staff. The PI (or designated trained site staff) is responsible for assuring the retrieval of all left-over study drug supplies following administration to participants.

A Study Monitor will perform initial and ongoing study drug accountability. The study drug inventory and accountability/dispensing records must be available for inspection by the Study Monitor during the study. Used containers of the study drug will be retained and sequestered per participant and cohort and made available to the Study Monitor during study drug reconciliation.

# 8.6 Destruction of Study Drug

When requested in writing by the Sponsor and following drug accountability and reconciliation, unused study drug supplies may be returned to the Sponsor or destroyed by the PI (or delegate), provided destruction does not expose humans to risks from the study drugs. Records shall be maintained of the return or destruction of the study drug materials. These records must show the identification and quantity of each unit returned or disposed, the method of destruction (taking into account the requirements of local law), and the person who returned or disposed of the study drug materials. Such records must be submitted to the Sponsor.

# 9 ADMINISTRATION OF STUDY TREATMENTS

Delegated blinded study site personnel will administer the study treatment to each participant. All study treatment will be administered as per the randomisation schedule. A second blinded staff member will witness the study drug administration.

Each participant will receive a single IM administration of MB05, EU- or US-Synagis®, via a syringe using manual injection.

Participants will be dosed while in a supine or semi-supine position, and administration of the IP will be performed in the clinical unit by an appropriately qualified staff member who is trained on the procedure(s) of administering each of the study treatments. The IM injection will be administered into the ventrogluteal muscle of the hip (preferred site) or vastus lateralis of the thigh (secondary site) (Figure 2). The injection should never be given into an area where the skin is tender, bruised, red or hard. In addition, the skin at the injection site should be free of blemishes, scars, heavy hair, veins, moles, skin conditions, sores or tattoos that have the potential to interfere with the detection of local reactions

Subjects are required to refrain from strenuous exercise for at least 72 hours post-dose.

# Figure 2. Anatomical Markers Used to Identify the Ventrogluteal Muscle and Vastus Lateralis of the Thigh Injection Sites

The skin at the site of injection will be disinfected, and the skin gently stretched around the injection site.

Insert the needle at a 90-degree angle using a dart-like action and depress the plunger slowly at a rate of approximately 1 mL / 10 seconds. Wait for 10 seconds to allow the drug to diffuse into the tissue and then quickly withdraw the needle.

Before injecting, the plunger will be pulled back to check that the position of the needle tip is not intravascular. In the event that blood is observed in the syringe, the IP must not be injected and the needle must be withdrawn. In this instance, the withdrawn dose must be quarantined, another syringe dispensed, and the injection administered at another site. The replacement syringe dispensed will be the same treatment arm as with quarantined dose.

Participants will be instructed not to rub the area after injection.

Refer to the Pharmacy Manual for further details regarding administration of study treatments for this study.

# 10 CONCOMITANT MEDICATIONS AND OTHER RESTRICTIONS

Compliance to these restrictions will be assessed prior to first dosing and throughout the duration of the study.

# **10.1 Concomitant Medications**

The use of concomitant medication during the study is prohibited, with the exception of medications used to manage AEs and contraceptives for WOCBP.

Participants will be instructed not to take any prescription or over-the-counter medication (including herbal products, diet aids, and hormone supplements) within 10 days or 5 half-lives of the medication (whichever is longer) prior to the first study drug administration (contraceptives, paracetamol and ibuprofen are permitted as defined in the study exclusion

criteria).

Paracetamol and Ibuprofen will be allowed for the treatment of headache or other pain at all other times during the study (doses and amounts per PI discretion).

If the need for concomitant medication arises to treat an AE, the Investigator should make decisions based on the participant's specific clinical factors.

Any concomitant medication that is taken by or administered to a participant during the course of the study must be recorded in the eCRF. The entry must include dose, regimen, route, indication and dates of use.

## **10.2 Vaccinations**

Live or live-attenuated vaccines are not permitted within 3 months prior to dose administration on Day 1, or during the study.

Other vaccines (including COVID-19 vaccines) are not permitted within 14 days prior to dose administration on Day 1 or within 14 days following dose administration on Day 1.

## 10.3 Contraception

Female participants of childbearing potential, with a fertile male sexual partner, must use an acceptable method of contraception (APPENDIX 4) from 30 days prior to dosing until at least 190 days after the last dose of study drug.

Male participants, when engaging in any sexual intercourse must agree to use a condom for at least 190 days after the first dose of study drug. In addition, when engaging in sexual intercourse with a female who may become pregnant must agree to have the female use an acceptable form of contraception (APPENDIX 4) 30 days prior to dosing until at least 190 days after the last dose of study drug.

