### 6.5 Study Duration

The total maximum study duration for each participant is 130 days, inclusive of screening and visit windows.

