  - b. when engaging in sexual intercourse with a female who may become pregnant, must agree to have the female use an acceptable form of contraception (refer to APPENDIX 4) from 30 days prior to dosing until at least 190 days after the last dose of study drug.
- 9. Have suitable venous access for blood sampling.
- 10. Be willing and able to comply with all study assessments and adhere to the protocol schedule and restrictions.

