## 11.1.6 Pregnancy Test

Women of childbearing potential (WOCBP) will have a serum human chorionic gonadotropin (hCG) pregnancy test at screening to determine their eligibility for participation in this study and at the EOS/ETV to confirm no exposure occurred in utero (EIU). A urine hCG pregnancy test will also be conducted at several timepoints during the study as indicated in the Schedule of Assessments (SoA). If a urine test is positive, pregnancy will be confirmed by a serum hCG test.

During their participation in this study, subjects must be instructed to notify the clinical site if they or their partner becomes pregnant.

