## 12 ASSESSMENT AND MANAGEMENT OF ADVERSE EVENTS

## **12.1 Adverse Event Definition**

An **AE** is any untoward medical occurrence in a patient or clinical investigation participant administered a pharmaceutical product and which does not necessarily have a causal relationship with this treatment. An AE can therefore be any unfavourable and unintended sign (including an abnormal finding), symptom, or disease temporally associated with the use of a medicinal (investigational or non-investigational) product, whether or not related to that medicinal (investigational or non-investigational) product (based on International Council for Harmonisation [ICH] definition)

Any AE where a causal relationship with the study treatment is at least a reasonable possibility (i.e., possibly/probably or definitely related), is referred to as an **Adverse Drug Reaction**.

An **SAE** is any AE that, at any dose:

- Results in death.
- Is life-threatening (The term 'life-threatening' in the definition of 'serious' refers to an event/reaction in which the participant was at risk of death at the time of the event/reaction; it does not refer to an event/reaction which hypothetically might have caused death, if it were more severe).
- Requires inpatient hospitalisation or prolongation of an existing hospitalisation (only hospitalisations that are longer than expected based on Investigator judgement, will be considered prolonged hospitalisations).
- Results in persistent or significant disability/incapacity (an AE that results in a substantial disruption of a person's ability to conduct normal life functions).
- Is a congenital anomaly/birth defect (A congenital anomaly/birth defect that occurs in the offspring of a participant exposed to the study treatment).

Medical and scientific judgement should be exercised in deciding whether other situations should be considered serious, such as important medical events that may not be immediately life-threatening or result in death or hospitalisation but might jeopardise the participant or might require medical or surgical intervention to prevent one of the other outcomes listed in the above definition. These should also be considered serious. Examples of such events are intensive treatment in an emergency room or at home for allergic bronchospasm, blood dyscrasias or convulsions that do not result in hospitalisation, or development of drug dependency or drug abuse.

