#### Table 7. Terms and Definitions Used in Assessing the Final Outcome of an AE

## 12.3 Procedures and Time Period for Detecting Adverse Events

The Investigator (or designee) is responsible for detection, recording and reporting of events that meet the criteria and definition of AEs.

As a consistent method of soliciting AEs, the participant shall be asked a non-leading question such as: "How do you feel"?

Detection and recording of study-related AEs and SAEs extends from the signing of the consent form until completion of the last study-related procedure (including follow-up for safety assessments).

Any pre-existing conditions or signs and/or symptoms present in a volunteer prior to any involvement in the study (i.e., before informed consent) should be recorded as medical history. Any change in health status that is reported or observed after informed consent but prior to starting study treatment and is deemed by the study Investigator to be "not related" to study procedures, will be documented as medical history. In addition, any change in health status, which is reported after informed consent by the volunteer, but started prior to informed consent and did not worsen, will be documented as medical history. Any worsening of a pre-existing condition that occurs following informed consent will be recorded as an AE.

A post-study AE/SAE is defined as any event that occurs outside of the nominal AE/SAE study

detection period. Investigators are not obligated to actively seek AE/SAE in former study participants. However, if the Investigator learns of any SAE, including a death, at any time after a participant has completed the study and he/she considers the event reasonably related to the study treatment, the Investigator will promptly notify the Sponsor.

Participants must be provided with an "Emergency Wallet Card" indicating the name of the study treatment, the study number, the Investigator's name and an emergency contact number.

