# 12.7 Exposure In Utero Management and Reporting

In instances of pregnancies or suspected pregnancies identified or reported for any female participant (or male participant's female partner), including a positive pregnancy test regardless of age, during participation in this study, the pregnant female participant (or the male participant's female partner) will be advised to notify her healthcare provider.

The Investigator will notify the Sponsor and designated study safety officer of this event and document the pregnancy on the EIU form as described in the study Pregnancy/EIU Report Form Completion Guidelines.

The Investigator shall obtain informed consent from the pregnant female participant (or male participant's female partner) in order to allow him/her to review relevant medical records and conduct follow-up throughout the gestational period and on the infant following delivery. The Investigator shall follow-up newborn infants that have been exposed to study treatment *in utero* for a minimum of 12 months. Upon discovery of any congenital anomalies (or neonatal deaths) the Investigator shall submit a follow-up report to the Sponsor (and study safety officer) using an SAE Form (as per study Safety Reporting Plan) including information regarding the status of the newborn. A miscarriage or abortion shall also be reported by the Investigator to the study Safety Officer (and the Sponsor) using an SAE Form.

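### The duty to report and follow pregnancies in Section 12.7 ends with participation (Day 99 ± 3), about 92 days before the required 190-day contraception period ends

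*Protocol*

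**What the plan says.** **Period in which pregnancy must be avoided.** Section 10.3 states that female participants of childbearing potential with a fertile male partner "must use an acceptable method of contraception (APPENDIX 4) from 30 days prior to dosing until at least 190 days after the last dose". Inclusion criterion 7 sets the same end point. Under criterion 8, male participants use a condom for at least 190 days and must "have the female use an acceptable form of contraception (refer to APPENDIX 4) from 30 days prior to dosing until at least 190 days". There is a single dose, so first and last dose coincide.

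**Notification by participants.** Section 11.1.6: "During their participation in this study, subjects must be instructed to notify the clinical site if they or their partner becomes pregnant". The lists for the end-of-study and early termination visits (21.5.6, 21.5.7) include a serum pregnancy test for women of childbearing potential but no instruction about later pregnancies.

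**Reporting and follow-up by the investigator.** Section 12.7 covers pregnancies or suspected pregnancies in a participant or a male participant's partner, "including a positive pregnancy test regardless of age, during participation in this study". For these the investigator notifies the sponsor, seeks consent to "conduct follow-up throughout the gestational period and on the infant following delivery", and follows exposed infants for at least 12 months. Congenital anomaly, neonatal death, miscarriage and abortion go on an SAE form.

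**After participation.** Under 12.3, adverse event recording stops at the last study procedure and investigators need not look for later events. They must tell the sponsor "if the Investigator learns of any SAE, including a death, at any time after a participant has completed the study" and they consider it reasonably related. Section 12.1 counts congenital anomaly as an SAE, explained as "A congenital anomaly/birth defect that occurs in the offspring of a participant exposed to the study treatment". Pregnancy itself is not listed.

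**End of participation.** The last visit is Day 99 ± 3. Section 6.5: "The total maximum study duration for each participant is 130 days, inclusive of screening and visit windows".

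**The concern.** The protocol sets its own risk period for pregnancy at 190 days, yet the section that makes an exposed pregnancy visible to the sponsor switches off at the last visit. Followed to the letter, a pregnancy first identified on, say, day 120 after dosing is one the participant was required to avoid, but 12.7 does not require anyone to report it or to follow mother and infant.

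The trigger is identification, not conception. A pregnancy conceived before the last visit and recognised afterwards is also outside 12.7. This matters most for partners of male participants, for whom no test is scheduled.

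What is at stake is safety information on exposed pregnancies and infants in the first human study of MB05. No endpoint, analysis set or bioequivalence conclusion is involved.

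**Working it through.** **Inputs**
- Contraception end point: at least 190 days after dosing (Protocol 10.3; 7.2, criteria 7 and 8).
- Last visit: Day 99 ± 3 (Protocol 6.2).
- Screening: up to 28 days (Protocol synopsis).
- Day numbering: dosing day is Day 1 and there is no Day 0 (SAP 4.3).
- Sample size: 141 (Protocol 13.1).
- Contraceptive failure: below 1% per year with proper and continuous use (Protocol Appendix 4).

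**Step 1. Reproduce the plan's duration.** 28 + 99 + 3 = 130 days, which matches Section 6.5. Participation therefore ends no later than Day 102.

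**Step 2. Length of the gap.** Days after dosing at the last visit = visit day − 1. Gap = 190 − (visit day − 1). Share = gap / 190.

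| Last visit | Days after dosing | Gap (days) | Share of 190 |
|---|---|---|---|
| Day 96 | 95 | 190 − 95 = 95 | 50.0% |
| Day 99 | 98 | 190 − 98 = 92 | 48.4% |
| Day 102 | 101 | 190 − 101 = 89 | 46.8% |

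The synopsis describes follow-up as running to 99 days after dosing. On that reading the gap is 190 − 99 = 91 days (47.9%), or 88 to 94 with the window. No reading closes it. After early termination the gap is longer; the documents do not say when withdrawals are expected, so no figure is given.

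**Step 3. Does another provision fill the gap?**

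| Event first known after the last visit | 12.7 | 12.3 |
|---|---|---|
| Pregnancy itself | Outside its trigger | Not an SAE |
| Healthy exposed infant | Outside its trigger | Not an SAE |
| Congenital anomaly | Outside its trigger | Notified if the investigator learns of it and considers it related |
| Neonatal death, miscarriage, abortion | Outside its trigger, though 12.7 assigns these outcomes to an SAE form | Can be notified on the same two conditions |

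**Step 4. Illustrative number of pregnancies.** Expected number = participants at risk × annual rate × gap / 365.
- All 141 at risk, 1% per year: 141 × 0.01 × 92/365 = 0.355, about 0.36. With the window: 141 × 0.01 × 89/365 = 0.344 to 141 × 0.01 × 95/365 = 0.367.
- A quarter at risk (an assumption; the documents give no share): 0.355 × 0.25 = 0.089.

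These are not upper bounds. The 1% figure presumes proper use, and the protocol schedules no check on use after the last visit.

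**The case against.** **11.1.6 may already reach beyond Day 99.** Its opening words can be read as dating the instruction and not as ending the duty to notify. This stands: a reader might infer that the protocol ends participants' duty to notify at Day 99, and the text does not establish that. But 12.7 is where the investigator's reporting and follow-up duties sit, and its limit is not ambiguous in the same way.

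**Follow-up already runs past Day 99.** True for a pregnancy captured on study, which is followed through gestation, and the infant for at least 12 months. The gap concerns pregnancies newly identified after participation.

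**There is a safety net.** Section 12.3 has no time limit, and the outcomes it can catch go beyond congenital anomaly. It remains passive, depends on a judgement of relatedness, and misses both the pregnancy and a healthy exposed infant.

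**Other documents may cover it.** Section 12.7 refers to pregnancy reporting guidelines and a Safety Reporting Plan, and participant instructions would normally sit in the consent form. None was available. A reader might infer that exposed pregnancies will go unreported in practice; the documents do not support that. The point is confined to the protocol text.

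**The importance is limited.** Two of the three arms receive a licensed product, Section 4.4 treats experience with it as applicable to MB05, and the illustrative count is below one. This bears on urgency. It does not justify a reporting period shorter than the protocol's own risk period.

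**Conclusion.** The point holds for the trigger in Section 12.7. For completers, a pregnancy newly identified in a participant or a male participant's partner falls outside the reporting and follow-up duty for about 92 of the 190 days (48%), or 89 to 95 days with the visit window. This rests on taking participation to end at the last visit, as Section 6.5 implies, and on the protocol text alone.

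It would go too far to say that no provision of any kind applies after Day 99: 11.1.6 is ambiguous and 12.3 catches some outcomes. Nor is 0.36 a worst case; it is what 1% per year would give if everyone were at risk. This is a gap in safety reporting, worth correcting, with no effect on the bioequivalence analysis.

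**What to change.** **Change**
- In 12.7, replace the limit to participation with *from dosing until 190 days after dosing*, for participants and for partners of male participants.
- In 11.1.6, state that participants must notify a pregnancy, their own or a partner's, until 190 days after dosing.
- Repeat that instruction at the end-of-study and early termination visits (21.5.6, 21.5.7).
- State who receives such reports after a site has closed, since 15.8 closes sites on study completion.
- State that this reporting does not delay study completion (15.8) or the final analysis (SAP 19.2). Section 15.8 defines completion by the last participant's last contact, so a day-190 contact counted as study contact would move both by about 92 days.
- Align the consent form, the pregnancy reporting guidelines and the Safety Reporting Plan if they differ.

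**Cost.** One protocol amendment with matching consent wording, and ethics approval if it is classed as substantial under 18.3. No visit, test or sample is added, and the follow-up procedure already exists in 12.7 for pregnancies captured on study.

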# 10.4 Caffeine, Tobacco and Alcohol

Participants will be instructed to abstain from consuming caffeine and/or xanthene products (e.g., coffee, tea, chocolate, and caffeine-containing sodas, colas) or alcohol for at least 24 hours prior to Day -1, and while confined to the clinical facility.

All subjects are required to abstain from smoking for 7 days prior to admission and during the confinement period.

Participants must have a negative result in a urine drug test and alcohol breath or urine test at screening and check-in (Day -1) and abstain from recreational drug use throughout the study.

# 10.5 Fasting Restrictions

Participants will be required to fast for at least 8 hours (water is permitted) prior to collection of clinical laboratory safety blood samples (except in the instance of an Early Termination Visit [ETV]).

## 10.6 Other Study Restrictions

The consumption of any foods containing poppy seeds should be avoided within 48 hours prior to screening and within 48 hours prior to admission to the clinical centre on Day -1.

Donation of >100 mL of blood or plasma is excluded within 4 weeks prior to the administration of study drug. Donation of blood products (except for sampling required for this study) or receiving blood products is not permitted throughout the period of participation in this study.

Subjects are required to refrain from strenuous exercise from 7 days before Check-in and within 7 days before non-residential visits and will otherwise maintain their normal level of physical activity during this time (i.e., will not begin a new exercise program nor participate in any unusually strenuous physical exertion). Subjects are also required to refrain from strenuous exercise for at least 72 hours post-dose on Day 1.

